ID: Pro00103863

Identifying the Optimal Neural Target for Misophonia Interventions

NCT04348591

Study protocol and statistical analysis plan

3/28/2023

Methods:

1. Participants and Procedures

This study was pre-registered under the Clinical Trials ID (NCT04348591) and ran between October 2020 and May 2022. The study was powered based on expected effect size derived from Kumar et al. [2], who compared misophonic participants ($n = 20$) with controls ($n = 22$) to find significant differences in AIC response, with an effect size of 1.27 (mean difference between groups = 2.7 a.u, $SD = 2.11$). For the proposed design, with planned comparisons across condition (downregulate, or listen), sound type (misophonic, aversive, or neutral) and group (misophonic vs. clinical control), and an expected effect size of 1.27, and alpha error rate set at .05, we expected adequate power (over 80%) with 29 participants in each group. Therefore, we aimed to recruit 30 participants in each condition.

Participants were recruited through online websites (e.g., Craigslist, Dukelist), social media (Facebook, Reddit), flyers, and electronic medical record outreach. Participants reached the study predominantly by seeing advertisements on social media and research websites. Many participants who met the severity cutoff for misophonia also found the study via self-guided internet search (see Table 1 for how participants who met the cutoff for each group of interest for the study found the study information).

Table 1. Recruitment methods and success rate in identifying the groups of interest for the study

Recruitment material used	Misophonia participants	Emotion dysregulation participants
Social media (Facebook, Reddit, Instagram)	33.46%	36.42%
Websites (Dukelist, Dukescience, Duke Misophonia website, Dukehealth)	30.08%	28.90%
Word of mouth (friend or medical professional referral)	13.16%	9.83%
Self-guided internet search (including finding the study on clinicaltrials.gov)	12.78%	13.29%
Volunteer registries (BIAC, ResearchMatch, CMER)	6.39%	6.36%
Outreach using electronic medical record	3.38%	4.62%
Newspaper	0.75%	0.58%

Note. Participants were included in the misophonic group if they scored ≥ 2 on the MQ subscales and indicated a severity higher than 6 on the MQ severity scale; participants were included in the emotion dysregulation group if they scored above 89 on the DERS scale.

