One hundred and twelve unique adults signed consent and participated in an in person screen to establish diagnostic profile, and examine any remaining inclusion/exclusion criteria (See Figure 1 for a visual depiction of the study design). We repeated the MQ and DERS at the in person screen and only

[figure not shown]

Figure 1. Experimental design

allowed participants in the study if the scales scores fit within our pre-determined parameters at the intake assessment. Twenty-two participants were no longer eligible at intake because their MQ and DERS scores changed sufficiently to be outside of the pre-determined cutoffs for the misophonic/clinical control groups. In addition, 19 participants were not eligible at the in person screen (see CONSORT) and 12 withdrew, were lost to contact before the experimental day, or couldn't do the MRI visit because of claustrophobia or technical difficulties. Thus, we had 59 enrolled participants for the study (enrolled group) of which 54 participants (completer group) were present for the neurostimulation experimental day (27 in each group).

Enrolled participants were 4 men and 52 women and 3 non-binary adults between the ages of 18 and 54 ($M = 28.31$; $SD = 9.06$ years old) who self-reported significant misophonic severity, or who met

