regressors: [listen to misophonic vs. aversive sounds], [downregulate vs. listen to misophonic sounds], [listen to aversive vs. neutral sounds], and [downregulate vs. listen to aversive sounds]. For all, the PPI was defined as the interaction between this event and the physiological regressor (66, 67). This method was performed for each subject and for each run. A third level analysis was then performed to assess the differences between groups. PPI analyses probe the synchronization of brain activity between two brain regions allowing us to differentiate regions which interact with each other versus work independently during experimental tasks (68). Whole brain Z image statistics (from both functional and PPI analyses) were thresholded using clusters determined by $Z > 2.3$ and a corrected cluster significance of $p = .05$ (69). Mixed-effects hierarchical linear models (MMANOVA) with analytically determined covariance structures were used to analyze the repeated measures data (70). All MMANOVA models used a restricted estimated maximum likelihood model to account for missing data (71) (i.e., cases with missing data were not discarded, but slopes for each participant were computed with the data available). Estimated marginal means (EMMs) were compared using LSD corrections for significant main and interaction effects, and are presented in the results section. For data that was not repeated, independent sample t -tests or non-parametric equivalents were employed. To test the neurobiological basis of misophonia, correlation analyses with neuroimaging data extracted from regions of interest (ROIs) and baseline behavioral measures were employed.

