To compare the effects our neurostimulation conditions, we conducted four analyses examining SUDS, peak GSR (SCR; peak arousal), SCL (tonic arousal), and HF-HRV. For the SUDS analyses, we examined the difference between SUDS at the end of each sound and the baseline SUDS collected after the task baseline. If task baseline SUDS were missing, session baseline SUDS were utilized instead. For the SCR analysis, the maximum value of the GSR during the presentation of each sound was used as outcome. For those two variables, the experimental group was used as a between-subject variable (misophonic or emotion dysregulation), and the experimental neurostimulation condition (active HF-rTMS over the right DLPFC, active LF-rTMS over the mPFC- insula, sham rTMS), the block instruction (downregulate misophonic, downregulate aversive, hear misophonic, hear aversive, hear neutral), the order effect of the 3 neurostimulation condition time within the task (0-2, corresponding with the runs employed), within the run (0-4, corresponding to each block), and within the block (0-3, corresponding to each of the sounds played), were used a within-subject variable. The experimental group by neurostimulation condition by block instruction interactions were entered as effects in the SUDS and SCR analyses. For SCR, the maximum GSR value during the habituation period was also controlled for. For the SCL and HF-HRV analyses, the experimental group and neurostimulation condition, and block instruction were also used but only the average within each block was used as outcome, time within block was excluded because HF-HRV requires at least 120s to be accurately assessed, and baseline values were added as main effects, time was considered a categorical variable. To account for multiple comparisons, we used a Bonferroni correction, and dropped the significance threshold to .0125. Differences between LF and HF rTMS were not hypothesized, but explored where both stimulation conditions were different than sham.

Planned covariates for all analyses included coil-to-cortex distance- given evidence that higher distance may impede the effectiveness of neurostimulation interventions for emotion regulation that are not designed to account for this parameter [77,78] - and data-driven covariates were also examined and added to these analyses as needed. Effect sizes were computed by using Feingold's formula [79] and interpreted using Cohen's specifications [80].

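### The single-step Bonferroni threshold of .0125 across the four stimulation analyses is valid, but Holm's step-down test keeps the same 5% bound and never rejects less

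*Combined protocol and SAP*

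**What the plan says.** Section 7 (Statistical Analyses) of the combined protocol and SAP defines the family: "we conducted four analyses examining SUDS, peak GSR (SCR; peak arousal), SCL (tonic arousal), and HF-HRV". It then sets the rule: "To account for multiple comparisons, we used a Bonferroni correction, and dropped the significance threshold to .0125". No step-down procedure, testing hierarchy or reason for the single-step form is given, and no simultaneous confidence intervals are planned. The only overall error rate in the document is in the power statement of Section 1 ("alpha error rate set at .05"), without sidedness.

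Three other statements in Section 7 bear on the point:

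- Each analysis is a model with several terms, not one test: "The experimental group by neurostimulation condition by block instruction interactions were entered as effects in the SUDS and SCR analyses".
- Follow-up comparisons inside a model are in effect unadjusted: "Estimated marginal means (EMMs) were compared using LSD corrections for significant main and interaction effects".
- The comparison of the two active conditions is exploratory: "Differences between LF and HF rTMS were not hypothesized, but explored where both stimulation conditions were different than sham".

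Section 7 lists HF-HRV and GSR as primary outcomes and SUDS during the stimulation session as secondary. All four analyses share the one .0125.

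**The concern.** Under the single-step rule each outcome must reach .0125 whatever the other three show. An outcome with p between .0125 and .05 is declared negative even when the other three hypotheses have already been rejected and their share of the 5% is no longer needed. Holm's procedure passes that share on.

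What is at stake is how many of the four outcomes can be claimed, including the primary ones, when stimulation affects several of them. The stimulation day had 27 completers per group, against an aim of 30. The validity of any rejection made under the present rule is not in question.

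**Working it through.** **1. The plan's figure.** With a 5% family and four analyses, .05/4 = .0125, so the threshold is reproduced. The sum is 4 × .0125 = .05. With four independent tests the family error would be 1 − (1 − .0125)^4 = 4.9%.

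**2. Holm's thresholds.** Order the four p-values and compare them in turn with .05/4 = .0125, .05/3 = .0167, .05/2 = .025 and .05/1 = .05, stopping at the first failure.

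**3. Holm loses no rejection.** If a p-value is at or below .0125, so is every smaller one. All of them pass their Holm thresholds, none of which is below .0125. Holm therefore reaches and rejects everything Bonferroni rejects.

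**4. The chance of any rejection is the same.** Both procedures reject something exactly when the smallest p-value is at or below .0125.

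**5. The bound is the same.** With m true nulls, the first false rejection comes at step 4 − m + 1 or earlier, so at a threshold of at most .05/m. Its probability is at most m × .05/m = .05, with no independence assumption.

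**6. Size of the gain.** The documents give neither effect sizes nor correlations for these outcomes, so these inputs are assumptions: two-sided z-tests; correlation .2 between outcomes, except .8 between peak GSR and SCL, which come from one skin-conductance signal; and a stated power at .0125 for each real effect. 400,000 draws per scenario:

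| Real effects | Power each at .0125 | Average power, Bonferroni → Holm | All real effects detected | Error on remaining nulls |
|---|---|---|---|---|
| 4 | 80% | 80% → 88% | 51% → 74% | none left |
| 3 (GSR pair and one other) | 80% | 80% → 84.5% | 60% → 71% | 1.2% → 4.1% |
| 2 (GSR pair) | 80% | 80% → 82% | 73% → 76% | 2.5% → 4.3% |
| 1 | 80% | 80% → 80.1% | same as average | under 5% with both |
| 4 | 65% | 65% → 75% | 29% → 52% | none left |
| 4 | 30% | 30% → about 35% | 4% → 13% | none left |

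No Bonferroni rejection was lost in any scenario. With nothing real, the family error is identical for both procedures, about 4.4 to 4.5%.

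**7. Sensitivity to the correlation.** With one common correlation of 0, .5 or .7, four real effects at 80% power give average power of 89.5%, 87.4% or 86.5% under Holm. The chance of detecting all four rises from 41% to 69%, 55% to 76%, or 62% to 79%. The gain does not hinge on the chosen correlation; it depends mainly on how many effects are real and how strong they are.

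**8. What the 5% covers.** It holds for one test per analysis, or separately for each effect taken across the four outcomes. As an illustration, two active-versus-sham contrasts in each of four analyses, all at .0125 and assumed independent, give 1 − (1 − .0125)^8 = 9.6%. This applies to Bonferroni and Holm alike.

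**The case against.** The strongest reply is that nothing in the plan is wrong: Bonferroni is valid, stated, and applied to all four analyses. That stands. A reader might infer that error control fails, or that the trial had less chance of a positive finding. The documents support neither, because the 5% bound is met and the smallest p-value faces .0125 under both rules.

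A reader might also say that power is given away for nothing. That goes too far. Within the 5% bound Holm spends more of the error: with three real effects, error on the fourth outcome rises from 1.2% to 4.1%.

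The shared skin-conductance signal is not an argument for Holm either. It makes both procedures equally conservative when nothing is real, and Holm does not exploit correlation.

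There are reasons to keep the single step. It judges each outcome without regard to the others, whereas under Holm a rejection on SUDS, a secondary outcome, relaxes the bar for the primary ones. It also matches simple 98.75% intervals (1 − .0125); an outcome significant only under Holm could have such an interval that includes zero. The first is a matter of preference. The second is a real but small cost, since no such intervals are planned.

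Two objections limit the remedy. No analysis has one decisive p-value, and Holm would let an outcome pass at up to .05 before unadjusted LSD comparisons follow. And the study ran from October 2020 to May 2022, with the text in the past tense, so loosening a declared rule after seeing results would be post hoc. Both stand and are built into the fix.

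**Conclusion.** The point holds as a matter of efficiency. Steps 3 to 5 are exact and need no assumption about this trial: Holm has the same bound, never rejects less, and leaves the chance of any rejection unchanged.

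The size is conditional. Under the assumptions in step 6, average power rises by about 8 points with four real effects at 80% power, 4.5 with three, 2 with two and almost none with one. At 30% power the gain with four real effects is about 5 points.

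A reader might take these figures as power this trial lost. The documents do not support that, since they give no effect size or correlation for these outcomes. The one planning effect size, 1.27 in Section 1, is a group difference in AIC response and says nothing about stimulation effects on SUDS, GSR or HF-HRV.

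Nor does either procedure hold 5% over all model terms and LSD comparisons; the bound holds per named effect. This is a worthwhile improvement, not the repair of an invalid test.

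**What to change.** 1. Name one effect per analysis that decides it, for example the stimulation effect, so that each of the four outcomes contributes one p-value.
2. Apply Holm across the four outcomes to that effect: .0125, .0167, .025 and .05 on the ordered p-values, stopping at the first failure. Report Holm-adjusted p-values.
3. State that the 5% family error applies to the named effect only, and that other model terms and LSD comparisons lie outside it.
4. If any of these p-values have been seen, keep the Bonferroni result as declared, report Holm beside it as a labelled post hoc sensitivity analysis, and reserve Holm as the main rule for a future plan.

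The cost is a few sentences and a second reading of existing p-values; naming the effect may need one extra contrast per model. If 98.75% intervals are reported, add a note that they may include zero for an outcome significant only under Holm.

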Manipulation Check: During the neurostimulation session we examined dissociation during each baseline and regulation period using a 4 item scale [49]. Participants were also asked to rate on a scale from 1 (I am certain I received sham stimulation) to 9 (I am certain I received active stimulation) their confidence in the assigned condition that they were kept blind to after each experimental trial. A rating of 5 indicated uncertainty. Before and after each experimental task (sounds, MRI, neurostimulation) we asked participants their current level of distress (rated on a scale from 1-7 [50]). After each experimental task, we also asked participants whether they were distracted or present and how successful they were in following the instructions.

Positive and Negative Affect Scale (PANAS). The PANAS [51] is a 28-item assessment of the degree to which the participant has felt a wide range of positive and negative emotions and feelings on the day of assessment. The items use a 5-point Likert scale ranging from 1 “Not at all or very slightly” to 5 “Extremely” with regard to the extent the participant has experienced each emotion. In this study, we examined changes in the PANAS negative affect scale before and after each experimental session in order to examine feasibility of proposed procedures. Cronbach’s alpha at before the intake session was .88.

Tolerability Questionnaire: Before and after the intervention session, participants were asked to rate on a scale from 0–3 (absent, mild, moderate, severe) the intensity of their headache, neck pain, scalp pain, seizure (as observed by technician), hearing impairment and any other side effect that they might have experienced from the TMS treatment.

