The experimental session (Figure 2C) included a 180s pre- session baseline, followed by three experimental runs, one using HF-rTMS over the right DLPFC (39 trains), one using continuous LF-rTMS over the right mPFC, and one using sham rTMS applied over one of those two targets, in a randomized order. Each run included a pre-task baseline (180s), a habituation period (180s) where neurostimulation was administered while the participant was not given any instruction, a sound task, including 5 blocks (600s), and a 600s break. Neurostimulation was administered throughout the sound task. Each block (120s long) started with an instruction (downregulate or listen) and was followed by four sounds played on repeat for 25 seconds (either misophonic, neutral, or aversive depending on the block). Sound and block order was randomized within each run. During the sound presentation a downward arrow (for downregulate), or wave symbol (~, for listen) was present on the screen to guide participants on what to do, neurostimulation and psychophysiological data collection was ongoing.

Psychophysiological Data

HR and GSR were recorded during the whole duration of the sound task and the neurostimulation session. AcqKnowledge software was used to collect and pre-process raw ECG data by using a built in automated heart rate variability (HRV) analysis tool that follows established frequency domain algorithm guidelines [75]. For each baseline, habituation, and 120s listen or down-regulate block, high frequency HRV (HF-HRV) was extracted to capture emotion regulation. Reactivity to emotional cues was captured through GSR. For each baseline, habituation period, and for each sound presentation we extracted the maximum GSR value as a measure of peak emotional arousal. We then removed from the GSR signal, with the help of a MATLAB program, skin conductance responses (SCRs) by leveling the signal when clear spikes were identified [76]. In this way, the tonic signal, or skin conductance level (SCL), was also extracted from each baseline, habituation to rTMS, and 120s listen/regulate block. SCL values represent average arousal during these distinct time periods.

7. Statistical Analyses

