Preliminary analyses, including *t*-tests and chi-squares, were conducted to assess demographic differences between experimental groups. We also examined any differences on matching variable (sex at birth, age) and other potential confounding variables like demographic characteristics, use of medication, dissociation during the experimental task, sleepiness during the experimental day, discomfort during neurostimulation, or psychophysiological effects induced by rTMS alone.

Primary outcomes set *a priori* were BOLD signal differences within the dlPFC and vmPFC during regulation of misophonic versus aversive sounds, BOLD signal differences within the AIC when listening to misophonic versus aversive sounds, change in HF-HRV and GSR during experimental blocks from baseline, acceptability of procedures as measured by percent of participants who complete the sessions. Secondary outcomes included self-reports (SUDS during the neurostimulation experiment, DERS, PROMIS-43), whole-brain BOLD changes when comparing aversive with neutral sound presentation and regulation, and when comparing misophonic with neutral sounds presentation and regulation.

To examine differences in functional activation between groups during the neuroimaging experiment, a group analysis was performed. Each functional and PPI FSL Level 2 analysis for each participant was entered into a third level FSL FEAT analysis assessing the differences between participants who in either the misophonia or the clinical control group.

To compare groups on functional connectivity during contrasts that were not included for targeting, four additional whole brain PPI analyses were performed using the same left insula seed, thresholded at 2.3, and then using the time series from this anatomical mask as the physiological regressor. In addition to the functional task regressors, each additional PPI analysis included one of the contrasts of interest as

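### The neurostimulation models admit covariates chosen from the data, and the SCR model adjusts for a value recorded while stimulation is on

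*Combined protocol and SAP*

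**What the plan says.** All of the following is in the combined protocol and SAP.

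- Section 7 (Statistical Analyses) names one covariate for every model: "Planned covariates for all analyses included coil-to-cortex distance". The same sentence goes on to say that "data-driven covariates were also examined and added to these analyses as needed".
- For the SCR model, Section 7 adds: "For SCR, the maximum GSR value during the habituation period was also controlled for". Section 6 (Neurostimulation Experimental Session) describes that period as "a habituation period (180s) where neurostimulation was administered while the participant was not given any instruction". Earlier in Section 7, the GSR primary outcome is defined as a change from baseline.
- The preliminary analyses in Section 7 examine possible confounders, among them "dissociation during the experimental task, sleepiness during the experimental day, discomfort during neurostimulation, or psychophysiological effects induced by rTMS alone".
- Section 3 (Measures, Manipulation Check) shows how often dissociation was recorded: "During the neurostimulation session we examined dissociation during each baseline and regulation period using a 4 item scale". The Tolerability Questionnaire is less frequent: "Before and after the intervention session, participants were asked to rate on a scale from".
- For the four neurostimulation outcomes (SUDS, SCR, SCL, HF-HRV), "we used a Bonferroni correction, and dropped the significance threshold to .0125".

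**The concern.** Each participant received high-frequency, low-frequency and sham stimulation in random order, so the active-versus-sham contrast is the randomised part of the study. Within it, a variable that arises once stimulation has started cannot be a confounder. It is either a consequence of stimulation or unrelated to it. Two things can go wrong if such a variable is adjusted for. If it lies on the path from stimulation to outcome, part of the real effect is removed. If it shares an unmeasured cause with the outcome (the participant's state during that run, for example), adjustment can produce an effect where there is none.

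The covariate rule is open to this because it does not restrict timing, and the SCR model does it explicitly. Separately, letting the data decide which covariates enter leaves several possible models per outcome. The .0125 threshold allows for four outcomes, not for a choice among models.

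**Working it through.** **The plan's own figure.** 0.05 / 4 = 0.0125, as stated. Four independent tests at that level give 1 − (1 − 0.0125)^4 = 0.049. The threshold is right for four models fixed in advance.

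**Which variables can matter.** In a within-person contrast, a covariate recorded once per session and entered as a main effect is the same in all three runs, so it cannot absorb the contrast.

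- Habituation GSR: one value per run, recorded under stimulation, and fixed in the SCR model. This is documented.
- Other habituation physiology (HF-HRV, SCL): one value per run, recorded under stimulation. Section 7 lists the bodily response to rTMS itself among the variables examined. Entry into a model is not documented.
- Dissociation: recorded per period, so it can differ by condition. Entry into a model is not documented.
- Discomfort and sleepiness: no per-run measure is described. The tolerability ratings bracket the whole session, and sleepiness refers to the day.

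**Size, under assumptions.** The documents give no covariate shifts or correlations, so these are assumed. The setting is 54 participants (the completers), a paired active-minus-sham difference, a test at .0125, and unit SD within a run. Runs are first taken as uncorrelated within person, so the difference has SD √2.

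Real effect of 0.50 SD, partly carried by the covariate: expected adjusted effect = 0.50 − slope × shift. The lowest and highest cases for shifts of 0.3 to 0.5 are 0.50 − 0.2 × 0.3 = 0.44 and 0.50 − 0.4 × 0.5 = 0.30. No true effect, covariate shifted by stimulation and sharing a cause with the outcome: spurious effect = −correlation × shift.

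| Shift (SD) | Slope or correlation | Adjusted effect (true total 0.50) | Simulated power, unadjusted → adjusted | Simulated null rejection, adjusted |
|---|---|---|---|---|
| 0.3 | 0.2 | 0.44 | 0.51 → 0.39 | 1.6% |
| 0.3 | 0.4 | 0.38 | 0.50 → 0.31 | 3.2% |
| 0.5 | 0.2 | 0.40 | 0.50 → 0.28 | 2.5% |
| 0.5 | 0.4 | 0.30 | 0.51 → 0.18 | 7.1% |
| 0.8 | 0.2 | 0.34 | 0.52 → 0.16 | 3.8% |
| 0.8 | 0.4 | 0.18 | 0.51 → 0.05 | 16.3% |

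Without adjustment, null rejection stayed between 1.0% and 1.4%.

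Hand check of the 0.5 / 0.4 null case:

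- Bias: −0.4 × 0.5 = −0.20.
- Residual SD of the difference: √2 × √(1 − 0.16) = 1.296.
- Standard error: 1.296 / √54 × √(1 + 0.25/2) = 0.187.
- Ratio: 0.20 / 0.187 = 1.07, against a critical value of about 2.585, which gives roughly 6.5%. This agrees with the simulation.

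If runs correlate 0.5 within person, the difference has SD √(2 × (1 − 0.5)) = 1. The standard error in the same case is 0.917 / √54 × √(1 + 0.25) = 0.140, and the ratio is 1.43. Rejection is then about 12% by hand and 13% by simulation. For shifts of 0.3 to 0.5 the range in that setting is about 2.0% to 13%.

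**Selection alone.** With no true effect and covariates that stimulation does not affect:

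- Covariate set chosen by the smallest stimulation p-value: 2.5% to 3.5% with three candidates, 4.1% to 11.1% with six.
- Covariates chosen by correlation with the outcome: 1.5% to 2.1%.

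With two run-level candidates shifted 0.2 to 0.5 SD, unrelated to the outcome and chosen by smallest p-value, the rate was 1.7% to 2.3%.

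**The case against.** The list of possible confounders sits among the preliminary analyses, which open with comparisons between the misophonia and control groups. Group is not randomised, so looking for confounders there is proper. The later sentence on data-driven covariates does not refer back to that list. A reader might infer that dissociation, discomfort and the bodily response to rTMS were adjusted for; the documents do not say so. This objection stands, and it is why the point rests first on the open rule and on habituation GSR. It also stands for discomfort: no per-run measure is described.

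A reader might also conclude that the .0125 threshold has failed. That does not follow. The inflation depends on a selection rule that is not stated, and it is small if covariates were chosen by correlation with the outcome. The sham coil was built to give similar sounds and scalp sensations, so a shift of 0.5 SD between active and sham is not a neutral assumption.

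Adjusting for habituation GSR can also be defended as asking a different question: the effect during sounds beyond the direct bodily response to rTMS. The adjustment was stated in the plan, not picked from the data. But that is a different estimand, it needs the further assumption that nothing unmeasured drives both GSR values, and the plan does not label it so.

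Much is already handled well. Run order is in the SUDS and SCR models, SUDS is taken as a difference from baseline, and baseline values enter the SCL and HF-HRV models.

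**Conclusion.** The concern holds in a limited form. Section 7 allows covariates to be chosen from the data for the four neurostimulation models, without a timing limit and without a commitment to show the models unadjusted. The SCR model adjusts for a value recorded under the very condition being compared. Both expose the active-versus-sham contrasts to bias toward or away from zero, and the first can raise the error rate above .0125.

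Whether either has happened, and by how much, cannot be read from the documents. Every figure above other than the .0125 check rests on assumed shifts, correlations, within-person correlation and selection rules, and shows only that the effect could be material at this sample size. The documents do not support a claim that the reported contrasts are biased or that stimulation-induced variables other than habituation GSR were used.

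**What to change.** Make the primary models those with a fixed covariate set: the pre-task baseline value for that run, run order and coil-to-cortex distance. For SCR, use pre-task baseline GSR in place of habituation GSR. The 180 s pre-task baseline in each run supplies this value, and it matches the definition of the GSR outcome as change from baseline. In the second and third runs that baseline follows an earlier run and a 600 s break, so a version using the pre-session baseline is a sensible additional check for carry-over.

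Report dissociation, discomfort and the bodily response to rTMS by stimulation condition, at the level at which each was recorded. Show models that adjust for habituation GSR or for data-driven covariates only as labelled sensitivity analyses, described as estimating the effect beyond direct rTMS physiology where that is the intent.

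The study ran until May 2022 and the document is dated March 2023, so new wording cannot restore pre-specification. What remains is to disclose, for each of the four models, which covariates were added and why, and to refit without them. The cost is SAP wording and a refit on existing data, with possibly slightly less precision than the data-driven models.
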